## 17. Use of Social Media

17.1. Types of social media to be used and how:

Study website: <https://rise.com> (team url = nest)

Parents will be invited to the website, provided a username and prompted to create a unique password. There will be no patient information on the website, and no means for synchronous communication. There will be a means of asynchronous communication (email) between the participant and PI during the study for questions or concerns.

Zoom video conferencing: UW HIPAA secure zoom account

A recurring zoom meeting will be scheduled weekly for parents to communicate directly with a yoga teacher. See 15.1 for privacy related to zoom

17.2. Measures in place to protect the privacy or confidentiality of subjects:

No identifying information regarding the patient (infant) will be shared during this study. Weekly zoom check-ins will be voluntary and for parents participating in the yoga intervention only, no names or patient information will be disclosed during these meetings.

17.3. Types of communications that will be submitted to the IRB for review:

Email communication with parents will be directed through REDCap and limited to periodic requests to fill out REDCap surveys during the study period, emails containing gift card links, and reminder emails.

17.4. If user-generated content will be active, how it will be monitored and what actions will be taken to ensure subject safety and study integrity:

No user generated content

## 18. Research Related Injury

18.1. Available compensation in the event of research related injury:

N/A

## 19. Recruitment Methods

19.1. When, where, and how potential subjects will be recruited:

**University of Washington and Seattle Children's Hospital:** All infants born <32 weeks gestation and/or <1500g or with a length of stay estimated to be >6 weeks, and who has been admitted to the University of Washington NICU or Seattle Children's NICU will be screened for eligibility by principal investigator ([name]).

A screening form (see other attachments) will be maintained on REDCap to document patients screened, reasons for eligibility/ineligibility, reasons for nonparticipation of eligible parents. A recruitment log (see other attachments) will be maintained in a password protected database located on the Seattle Children's server containing MRN of enrolled infant, record ID of parent participant and date of consent for data collection purposes. PI will send secure email with names of patients who meet inclusion criteria to weekly attending of record for final approval to contact (re: patient/parent stability). PI or representative (resident/fellow or APP caring for infant) will make first contact with parent with a standardized bedside conversation or phone

call to explain study. If family is interested in more information PI will meet family in person in the NICU at least 10 days after admission. Following consent, the introductory survey and first set of self-report scales will be completed during enrollment process.

Participants in the intervention group will be guided on how to log into the study website, and will be instructed to respond to emails with links for self-report scales to be completed throughout the study period. Participants in the control group will be instructed to respond to emails with links for self-report scales to be completed throughout the study period. The first week of intervention will begin on the Monday after enrollment or 10-14 days after infant admission to the NICU.

Note that UWMC is a birth hospital, thus 10 days after admission will likely be 10 days of life. Infants are typically referred/transferred to SCH NICU from other NICUs, and thus 10 days after admission may reflect different ages. The inclusion criteria for both institutions will be the same.

19.2. Steps that will be taken to protect privacy during the recruitment process:

Site enrollment log will be maintained in a password protected database located on the Seattle Children's server. Screening form will be maintained by the site PI on a secure REDCap database, and will contain the following information: Record ID, screening date, mother/father, eligibility (yes/no), attending approval to enroll (y/n), whether they were enrolled, and if not enrolled, the reason why. If the parent is enrolled as a study participant, document that consent was obtained, and the study ID number. MRN numbers of infants will be stored on a separate recruitment log in a password protected excel sheet on the Seattle Children's server. MRN number is required to access infant demographic information.

19.3. Sources of subjects:

All parents of infants born <32 weeks gestation or <1500 grams will be screened by study coordinator.

Subjects will be recruited by screening of the electronic medical record (EPIC) at the University of Washington and Seattle Children's NICUs

19.4. Methods that will be used to identify potential subjects:

See 19.1

19.5. Materials that will be used to recruit subjects:

A Study poster will be used to inform staff, faculty, and parents about the study. Posters will be available in the NICU Attending office and NICU Staff lounges and staff bathrooms at both institutions to increase awareness of the study

19.6. Recruitment methods not controlled by Seattle Children's:

N/A

## 20. Consent/Assent/Permission

20.1. Consent/assent/permission process:

The Attending health care provider will approve the research coordinator to meet and discuss the study with potential subjects. If either parent is interested in learning more about the study,

the research coordinator or investigator will be notified so they can discuss the study with the parent and seek consent in person. Investigators will only approach a family after infant's attending health care provider gives permission and family indicates that they are interested in further information about the study. The parent may withdraw from study at any time. Investigator will retain the original signed document, and a copy will be provided to the subjects. Consent for participation must be obtained after the baby is at least 10 days of age (UWMC) or has been admitted at least 10 days (SCH). An identical consent form will be presented by the research coordinator to both control and intervention groups reviewing the practice of yoga, meditation and breathing exercise as well as the details of the study.

20.1.1. Alternative way of obtaining consent/assent/permission information for individuals who are not able to receive/access/use the electronic consent system being used or explanation as to why an alternative process is unnecessary:

Consent form will be signed on paper, no electronic consent system will be used. Any initial parent REDCap surveys or demonstration of the study website will be done on iPads made available specifically for parents participating in the YIN study.

20.1.2. Where the consent/assent/permission process will take place:

At the site where infant is admitted (UWMC or SCH NICU) in person with parent(s).

20.1.3. Steps that will be taken to protect privacy during the consent/assent/permission process:

Consent discussion will take place in patient's individual room or private conference room if available, keeping in mind the privacy of the parent and infant.

20.2. Plan for documenting consent/assent/permission:

Consent will be documented in writing on a paper form provided at the time of the consent conversation. REDCap screening form will document date of consent. REDCap randomization form will record date of randomization and outcome of randomization (Group A or B).

20.2.1. Plan to confirm that the individual who provides the electronic signature is the subject (or their parent/LAR), when the signature is not personally witnessed by a member of the study team or explanation as to why such a plan is unnecessary:

Study coordinator will only receive actual signatures of participants on paper consenting forms. NO electronic signature will be used.

20.2.2. If using electronic consent, plan to manage consent documentation over the life of the study in a way that maintains integrity and accessibility:

N/A

20.2.3. If consent/permission will be documented in writing (check one):

"SOP: Written Documentation of Consent (HRP-091)" will be followed.

"SOP: Written Documentation of Consent (HRP-091)" will not be followed.

Process of documenting consent:

N/A

20.2.4. If consent/permission will not be documented in writing (check all that apply, *complete Section 21.13 to request a Waiver of Documentation of Consent*)

- A written statement/information sheet describing the research will be provided to subjects.
- A written statement/information sheet describing the research will not be provided to subjects. Explain: N/A
- A consent script will be used.

20.3. Waiting period available between approach and obtaining consent/assent/permission:  
N/A

20.4. Process to ensure ongoing consent/assent/permission:  
N/A

20.5. If this box is checked, "SOP: Informed Consent Process for Research (HRP-090)" will be followed:

20.6. If "SOP: Informed Consent Process for Research (HRP-090)" will not be followed, address the following:

20.6.1. Role of the individuals listed in the application as being involved in the consent process:  
N/A

20.6.2. Time that will be devoted to the consent discussion:  
N/A

20.6.3. Steps that will be taken to minimize the possibility of coercion or undue influence:  
N/A

20.6.4. Steps that will be taken to ensure the subject's understanding:  
N/A

#### 20.7. Individuals who use a language other than English

20.7.1. Presentation of Research Information and Documentation:

- Appendix A-10 of the Investigator Manual will be followed
  - Short form procedures may be used per HRP-091. If so, choose applicable box(es):
    - Per section 5.5.1
    - Per section 5.5.2
- Appendix A-10 of the Investigator Manual will not be followed. Explanation of procedures not following Appendix A-10:

#### 20.8. Subjects Who Are Not Yet Adults (Infants, Children, Teenagers)

20.8.1. Process used to determine whether an individual has not attained the legal age of consent under the applicable law of the jurisdiction in which the research will be conducted (e.g., individuals under the age of 18 years):

Parents under the age of 18 will be excluded from participation. Individuals will be asked their age at the time of enrollment. Since to be included in the study, minors

must be infants in the NICU, no additional process is needed to determine whether they have reached the age of majority.

20.8.2. Parental permission will be obtained from:

- Both parents unless one parent is deceased, unknown, incompetent, or not reasonably available, or when only one parent has legal responsibility for the care and custody of the child.
- One parent even if the other parent is alive, known, competent, reasonably available, and shares legal responsibility for the care and custody of the child.
- Neither parent.

20.8.3. Process used to determine an individual's authority to consent to each child's general medical care if permission will be obtained from someone other than parents:

N/A

20.8.4. Assent will be obtained from:

- All children.
- Some children. Specify: N/A
- None of the children. Explain: subjects are neonates, intervention for parents

20.8.5. Procedures for obtaining and documenting assent:

N/A

20.8.6. Plan for re-approaching children who have reached the age of majority to obtain consent:

N/A

**20.9. Cognitively Impaired Adults/Adults Unable to Consent**

20.9.1. Process used to determine whether an individual is capable of consent:

N/A

20.9.2. Individuals from whom permission will be obtained in order of priority:

N/A

20.9.3. Assent will be obtained from:

- All of these subjects.
- Some of these subjects. Specify: N/A
- None of these subjects. Explain: N/A

20.9.4. Process for obtaining and documenting assent:

N/A

**20.10. Waiver or Alteration of Consent/Assent/Permission**

20.10.1. Reasons for requesting a waiver or alteration of informed consent/assent/permission:

N/A

- 20.10.2. Consent/Assent Waiver/Alteration Criteria justifications:
- 20.10.2.1. The research involves no more than minimal risk to the subjects because:  
N/A
- 20.10.2.2. The waiver or alteration will not adversely affect the rights or welfare of the subjects because:  
N/A
- 20.10.2.3. The research could not practicably be carried out without the waiver or alteration because:  
N/A
- 20.10.2.4. If the research involves using identifiable private information or identifiable biospecimens, the research could not practicably be carried out without using such information or biospecimens in an identifiable format because:  
N/A
- 20.10.2.5. Whenever appropriate, the subjects will be provided with additional pertinent information after participation:  
N/A
- 20.10.3. If the research involves a waiver of the consent process for emergency research, provide sufficient information for the IRB to make its determinations:  
N/A
- 20.11. **Waiver of Written Documentation of Consent/Permission (address one option):**
- 20.11.1. Option 1:
- The research involves no more than minimal risk to the subjects because:  
N/A
  - The research involves no procedures for which consent is normally required outside of the research context because:  
N/A
- 20.11.2. Option 2:
- The principle risk of a signed consent document would be the potential harm resulting from a breach of confidentiality because:  
N/A
  - Both are true:
    - The only record linking the subject and the research would be the consent document
    - The subject or LAR will be asked whether the subject wants documentation linking the subject with the research, and the subject's wishes will govern.
- 20.11.3. Option 3:
- The research involves no more than minimal risk to the subjects because:  
N/A

- The subjects or LARs are members of a distinct cultural group or community in which signing forms is not the norm. Explain:  
N/A
- There is an appropriate alternative mechanism for documenting that informed consent was obtained. Explain:  
N/A

## 21. HIPAA Authorization and RCW Criteria

### 21.1. HIPAA Authorization (check all boxes that apply):

- The study does not involve the receipt, creation, use and/or disclosure of protected health information (PHI).
- HIPAA authorization will be obtained as part of a signed consent form.
- The study will access PHI without prior authorization from subjects (including for recruitment purposes – e.g., reviewing the medical record to determine eligibility). *Complete Section 21.2 to request Waiver of HIPAA Authorization.*
- Subjects will review a written statement/information sheet with the appropriate HIPAA language but will not provide a written signature. *Complete Section 21.2 below to request an Alteration of HIPAA Authorization.*
- Other. Explain:  
N/A

### 21.2. HIPAA Waiver/Alteration Criteria:

#### 21.2.1. Reasons for requesting a waiver or alteration of HIPAA Authorization:

Research coordinator or designee will review medical record to determine eligibility for this study.

#### 21.2.2. The use or disclosure of PHI involves no more than a minimal risk to privacy of individuals, based on, at least the presence of the following elements:

##### 21.2.2.1. An adequate plan to protect the identifiers from improper use and disclosure:

Record ID, screening date and parent surname, parent email address will be saved in the screening form, and additional data regarding demographics and characteristics of NICU baby and parent will all be collected and stored in a secure REDCap database. Infant surname and MRN will be stored in a recruitment sheet located in a password protected file on the Seattle Children's Server.

##### 21.2.2.2. An adequate plan to destroy identifiers at earliest opportunity consistent with conduct of research:

Identifiers saved in REDCap and SCH server will be destroyed within one year of collection.

##### 21.2.2.3. Assurances that PHI will not be reused or disclosed to any other party or entity, except as required by law or for authorized oversight of the research:

PHI collected will not be reused or disclosed to any entity, except as it relates to concerns for parent safety (e.g., unit social worker will be

contacted if depression or anxiety scales are concerning and further intervention for parent is advised).

- 21.2.3. The research could not practicably be conducted without the waiver or alteration of authorization:

Without the waiver, screening for eligibility would not be possible. All parents of infants in the NICU would need to be approached, which would unnecessarily burden those who are ineligible for the research.

- 21.2.4. The research could not practicably be conducted without access to and use of the PHI:

This research requires the screening of patients in the NICU prior to consent to target the study to the appropriate population.

## 22. Payments/Costs to Subjects

- 22.1. Amount, method, and timing of payments to subjects:

Parents participating in both control and intervention groups will receive a total of \$50 in gift cards (tango cards) during the course of the study:

- \$20 after completing 1 week of intervention, Intro survey, DASS21, first PSS:NICU.
- \$10 after completing 3 weeks of intervention and second PSS:NICU
- \$20 after completing 6 weeks of intervention, second DASS21, third PSS:NICU, PBQ, course completion survey

Distribution of tango cards will be done via email by the study coordinator and tracked in both a REDCap form and an excel sheet using participant randomization number and record ID (see other attachments)

Each family or pair of participants (partners) may receive only one set of gift cards totaling \$50. This will be made clear in the study consent form and parent information sheets.

- 22.2. Reimbursement provided to subjects:

- 22.3. Additional costs that subjects may be responsible for because of participation in the research:

Free WiFi is available for participants if logging into the study website from UWMC, SCH, Hotel Nexus, or the Ronald McDonald house. Study coordinators are unable to determine if free WiFi will be available if participants log into the study website from another location not listed above.

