## 3. Study Endpoints

### 3.1. Primary and secondary endpoints:

Goal would be to enroll parents of NICU inpatients from UWMC and SCH into the study on a rolling basis for 4-6 months or until we have enrolled a total of 20 parents to the intervention and 20 parents to the control groups spanning both institutions. The intervention lasts for a duration of 6 weeks.

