## 5. Procedures Involved

### 5.1. Study design:

This will be a randomized controlled pilot study to elucidate the optimal research strategy with which to implement mind and body interventions for **parents** of NICU patients, at 2 sites (University of Washington NICU and Seattle Children's Hospital NICU) comparing: 1) control group 2) yoga intervention (i.e: breathing exercises + meditation +postures).

Parents will be enrolled in the study after day 10 of infant admission to NICU and begin participation by day 14 of NICU admission (see Recruitment methods section 19).

The non-birth parent will be invited to participate in this study and may participate without the birth parent. If both parents are participating the partner would be randomized to the same group (control or intervention) see randomization section 5.2. In the circumstance that the birth parent declines participation and non-birth parent consents to participation, we will still obtain consent from parents to access infant medical records, however we will not obtain birth parent EPDS scale (see section 5.2)

If an infant is transferred from UWMC to SCH as part of their clinical care, a parent enrolled initially at UWMC may continue participation in this study while infant is admitted at SCH.

**Control group:** Parents will experience usual care including all available parental support as practiced in the specific site NICU. We will utilize a 'waitlist' control model for this project, whereby the parents randomized to control group will have unlimited access to the online platform hosting the yoga intervention following the completion of the study period.

**Intervention group:** In addition to usual care, the parents randomized to the intervention group will be provided a yoga mat and participate in 30-min online led yoga sessions done at least twice weekly at the parent's pace using a secure, virtual platform (website). There will be 6 total yoga classes (one introduced per week for a 6 week period). Each yoga session will be divided into three components, which will vary in duration based on a curriculum designed *specifically* with the post-partum state of mothers in mind:

- **Yoga postures (Asana)** = low impact gentle postures meant to be done individually
- **Breathing techniques (Pranayama)** = deliberate modifications of breath such as rapid

- diaphragmatic breathing, slow/deep breathing, alternate nostril breathing, breath holding

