## 5.2. Research procedures:

**Screening:** see section 19

**Randomization:** The parent(s) who consent to participate in the study will be randomized using a 2x2 computerized block randomization ([www.sealedenvelope.com/simple-randomiser/v1/lists](http://www.sealedenvelope.com/simple-randomiser/v1/lists)). Participants will be stratified by NICU into two groups A) usual care B) yoga intervention. At the time of consent, the study coordinator will be **blinded to the randomization**, and the parent will be presented with a sealed envelope that identifies group A (control) and group B (intervention).

When both parents from the same family are eligible and interested in study participation, both will be consented and then randomized to the same group and followed separately with outcome surveys. Since parental outcomes are likely correlated. Prior to randomization we will ask parents to designate one parent as the primary study participant. Outcomes of the parent designated as the secondary study participant will be included in exploratory analyses that appropriately accounts for potentially correlated outcomes.

**Intervention Group:** Parents will receive an information sheet (see 'Welcome Packet YOGA GROUP' in "other attachments" ) explaining the practice of yoga, meditation and breathing exercises, FAQs about the study including how to access an electronic tablet while in the unit (if parent is unable to supply their own device), instructions on how to access study website and Zoom. Parents will also sign the study consent form and HIPAA authorization, receive a personal yoga mat, ear-pods (if needed), and details regarding compensation for the study (see 23.1). Participants have the opportunity to keep the ear-pods and yoga mat at the conclusion of the study. Parents in the intervention group will receive usual care for parent support offered in site NICU and be enrolled in a 6-week virtual yoga curriculum (see description in 5.1). They will also be asked to periodically fill out questionnaires throughout the study.

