**Control Group:** Parents will sign the study consent and HIPAA forms. Information will be provided regarding the waitlist control model (see 5.1), and details about the compensation for the study (see 23.1). Parents in the control group will receive usual care for parent support offered in site NICU. They will also be asked to periodically via email to fill out identical questionnaires as the intervention group throughout the 6-week study period.

In general, a participating non-birth parent may skip self-report items that are considered not applicable, however there should be very few items that cannot be answered by either parent.

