5.4. Data to be collected, including long-term follow-up data:

**Infant Demographics:** gestational age (weeks), birth weight (g), postnatal age at enrollment and discharge (days)

**Infant characteristics:** Apgar score (5 min), inborn (n), multiparous birth (n), primary and secondary diagnoses (BPD, NEC, PDA, RDS, GI/GU, cardiac, other), IVH (grade), mechanical ventilation at study start (y/n), length of assisted ventilation (days), length of stay (days), any breastfeeding at discharge (y/n)

**Parent Demographics:** age, ethnicity, race, highest level of education, employment status, marital status, other children at home, mode of delivery (vaginal/c-section), experience with yoga before and during pregnancy

**Parent characteristics:** Edinburgh Postnatal Depression Scale scores (located in the infant EPIC chart (UWMC) or the maternal EPIC chart (SCH), or administered by study coordinator at time of enrollment)

**Parent study data:** YIN Introduction Survey, EPDS (if not administered by unit social worker) DASS21, PSS:NICU, PBQ, post-study questionnaire, participation in yoga intervention (tracked on rise website): sessions started (n), duration of participation (min)

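### Does tying the gift cards in both arms to completed weeks of intervention make the payment rule unworkable for controls, or threaten follow-up?

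*Protocol*

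**What the plan says.** Protocol 22.1 opens with a statement covering both arms: "Parents participating in both control and intervention groups will receive a total of" 50 dollars in gift cards. One list of three instalments follows, with no separate terms by arm:

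- 20 dollars after 1 week of intervention, with the introductory survey, DASS21 and first PSS:NICU;
- 10 dollars "after completing 3 weeks of intervention and second PSS:NICU";
- 20 dollars "after completing 6 weeks of intervention, second DASS21, third PSS:NICU, PBQ, course completion survey".

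Controls receive usual care during the study. Under the waitlist model in 5.1 they get "unlimited access to the online platform hosting the yoga intervention following the completion of the study period". For compensation details, 5.2 sends the reader of each arm's description to section 23.1, which deals with community-based settings and is marked not applicable. Section 5.4 lists sessions started and minutes of participation as the yoga data. The protocol does not define a completed week of yoga.

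**The concern.** Taken literally, the list asks controls for something they cannot do. They have no weeks of intervention to complete, so they would fail every instalment, against the promise in the opening sentence.

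A second possibility would matter more to a statistician. A coordinator might pay controls by the calendar, as the opening sentence implies, but require actual practice of yoga parents. Yoga parents who stopped practising would then lose the incentive to return the later forms, while controls would keep it. Those forms carry every post-baseline self-report outcome: the PSS:NICU at 3 weeks, and the DASS21, PSS:NICU and PBQ at the end. Missingness related to adherence in one arm only could distort the comparison. It would also blur what the adherence figures mean for the later trial.

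The wrong cross-references add to the doubt, because a reader who follows them finds no payment terms.

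**Working it through.** **The plan's own figure.** The instalments in 22.1 sum to 20 + 10 + 20 = 50 dollars, which is the stated total.

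**What each reading pays a parent who returns every form**

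| Reading of a week of intervention | Yoga parent | Control parent | Agrees with the opening sentence of 22.1? |
|---|---|---|---|
| (a) Elapsed study week | 50 | 50 | Yes |
| (b) Yoga practised, both arms | 50 if practising | 0 | No |
| (c) Yoga practised, yoga arm only | 50 if practising | 50 | Only if the same words mean different things by arm |

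Under (c), the money attached to follow-up forms is 10 + 20 = 30 dollars. The first 20 dollars is attached to forms which, under 19.1, are filled in at enrolment, so it cannot affect follow-up.

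**Which reading the protocol supports**

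1. The opening sentence of 22.1 covers both groups, and one list serves both. Reading (b) would defeat that sentence.
2. Section 3.1 treats the intervention as a stretch of time: "The intervention lasts for a duration of 6 weeks". Section 8.1 gives 6 weeks of participation for every subject, and 5.2 has controls answering the same questionnaires over a 6-week study period.
3. The second and third instalments fall at 3 and 6 weeks. These are the midpoint and final survey times in 5.2, and they are common to both arms.
4. Section 11.3 pays a parent who withdraws for the part of the study completed. It does not mention yoga completed.
5. Section 19.1 dates the first week of intervention from the Monday after enrolment, or from 10–14 days after the infant's admission. It names no arm and comes directly after the instructions to both. That is a calendar use of the phrase.
6. No threshold for a completed week of yoga exists anywhere, and 5.1 leaves sessions to the parent's own pace. The gift-card tracking in 22.1 uses the randomization number and record ID and mentions no yoga data. A practice condition would need a threshold and a data link, and the protocol has neither.

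All six points fit reading (a). Reading (c) requires one phrase in one bullet to be a calendar label for controls and a performance condition for yoga parents, and no arm-specific term supports that.

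**Whether stopping yoga stops the surveys.** Sections 15.1 and 17.3 send survey links by REDCap email, and 19.1 tells both arms to answer them. Nothing makes sending a form depend on yoga, so a parent who stops practising still receives the remaining questionnaires.

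**The case for a change.** The best case for a change is that the harmless reading is never stated. Section 5.2 has a neutral term available, the study period, and 22.1 does not use it. By joining completed weeks to completed forms in one clause, 22.1 can sound as though both are tasks. Section 11.3 deals with leaving the study, not with giving up yoga while still returning surveys. The pilot is small: 10.4 enrols 20 per arm against 16 needed, a margin of 20 − 16 = 4, so uneven loss of follow-up would hurt. New wording would cost little and leave the maximum at 50 dollars.

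Part of this stands. The wording is loose, and the reference to 23.1 is wrong in both places. The inference to damaged data does not stand. The 30 dollars is at stake only under reading (c), which is conjecture. No figure in the protocol links a lost instalment to a missing form, so setting it beside the margin of 4 shows nothing about power. The consent form and parent information sheets, which are what parents act on, are not available here and may already state the terms plainly.

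**Conclusion.** No change to the plan is needed. The phrase in 22.1 is imprecise for a control arm, but its context points to elapsed study weeks. On that reading the rule works as intended, with up to 50 dollars in either arm and nothing forfeited for lack of practice. Whoever issues the gift cards would fill this gap sensibly. The pointer to 23.1 is a clerical slip, and the terms are easily found one section earlier.

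The effect on sample size, power and the planned comparison is nil on the natural reading. On the only harmful reading it cannot be estimated from the protocol. The conclusion assumes that payments are administered by study week in both arms, and that the consent form and information sheets do not set a practice condition for the yoga arm. Neither can be checked from the protocol, but nothing in it suggests otherwise.
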